##### **2.4.7.1 Analyses of adverse events**

###### **2.4.7.1.1 Definitions**

Adverse events continuing from the original study into the entry into this extension study will be identified, and will be reported as one AE avoiding duplication of the same AE in two database. Adverse event summaries will include the number of events (N), number (n) and percentage (%) of patients experiencing an adverse event. The denominator for computation of percentages is the safety population. Sorting order will follow the internationally agreed MedDRA system organ

class (SOC) order, and further by decreasing number of events overall in preferred terms (PTs) within SOCs. When more than one PT has same number of events within the same SOC, the order of presentation will be alphabetical in PTs.

Treatment-emergent adverse events (TEAEs) will be defined as AEs that started during the on-treatment period – either in this study or in the original study.

If an AE date/time of onset is incomplete, an imputation algorithm will be used to classify the adverse event within the appropriate adverse event period. The algorithm for imputing date/time of onset will be conservative and will classify an adverse event as treatment emergent unless there is definitive information to determine otherwise. Details on classification of AEs with missing or partial onset dates are provided in [Section 2.6.2](#). If an AE worsens in severity, only the worst severity is captured on the AE log page in the e-CRF.

The AE log page in the e-CRF captures the date when the event became serious. If and when this date is non-missing, it indicates that the AE started as non-serious and became serious at a later date. To account for non-serious and serious parts of the AE collected in one AE log page, this AE will be split into two AEs - one non-serious, and one serious AE - with the same AE number, with the following modifications in data for these two AEs:

- Non-serious AE: AE end date, AE outcome, date of death or hospitalization, autopsy information, criterion for serious adverse event (SAE) will be blank.
- Serious AE: AE start date will use the date the event became serious.
- Action taken towards study drug and action taken (toward AE) will be considered in relation to the date the event became serious, the last infusion date and dosing information, and a determination will be made, in consultation with safety monitor of the trial, as to whether the recorded fields belong to non-serious AE or serious AE; then the decision will be implemented in analysis. Any such decision will be rationalized in the CSR.

For treatment-emergent AEs, separate listing of AEs, SAEs and IARs that started only after the first infusion in this extension study will be provided.

Start day of treatment emergent AE relative to first infusion = Start date of AE – first infusion date + 1

Start day of treatment emergent AE relative to last infusion = Start date of AE – last infusion date + 1

Total patient year for each group will be calculated and displayed on selected AE tables.

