10.5 OBLIGATION OF THE INVESTIGATOR REGARDING SAFETY REPORTING

The investigator is the primary person responsible for making all clinically relevant decisions on safety issues.

Any abnormal findings that meet the definition of an AE per [Section 10.5.1](#) will be recorded on the CRF. The investigator will continue to monitor the patient until the parameter returns to baseline or until the investigator determines that follow-up is no longer medically necessary.

All AEs (as described in [Section 10.5.1](#)) regardless of seriousness or relationship to study treatment will be collected from the time of written informed consent until the patient completes participation in the study as defined in [Section 6.3.1](#). Adverse events that started during the previous study which are ongoing at the time the patient signs the written informed consent should be reported in this study.

All SAEs (as described in [Section 10.5.1.2](#)) and any AESI requiring immediate notification (as described in [Section 10.5.2.3.1](#)) including those ongoing at the time of study completion will be monitored until resolution, stabilization of the condition, or until it is mutually agreed upon by both the investigator and the sponsor safety physician to discontinue.

If, at any time after the patient has completed participation in the study (as defined in [Section 6.3.1](#)), the investigator or study staff becomes aware of an SAE that they believe is possibly related or related to IMP, then the event and any known details should be reported promptly to the sponsor. Follow the reporting instructions in [Section 10.5.2.2](#).

All AEs diagnosed by the investigator will be reported per applicable regulations and guidelines. Definitions for AEs, SAEs, AESI; and instructions for AE monitoring and reporting, are provided in [Section 10.5](#) through [Section 10.8](#). All AEs will be coded using the version of Medical Dictionary for Regulatory Activities (MedDRA) currently in effect at the time of the considered database lock.

The investigator is responsible for reviewing and signing all laboratory reports. Any abnormal findings that meet the definition of an AE per [Section 10.5.1](#) will be recorded on the CRF. The investigator will continue to monitor the patient until the parameter returns to baseline or until the investigator determines that follow-up is no longer medically necessary.

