#### **2.4.7 Analyses of safety data**

The safety results will be presented using the safety population. Unless specified otherwise, the displays will include the original study data along with data collected in this study. Patients will be summarized and displayed by original study identifier, age cohort and overall. Safety data will be reported up to and including the time of treatment withdrawal, and follow-up for AEs, where applicable. The baseline value is the last available value before the first infusion of olipudase alfa in the original study, except for hematology parameters and possibly ECG parameters. For complete definition of baseline, refer to [Section 2.6.1](#).

For all safety data, the observation period in this study is the **on-treatment period**, which is defined as the time from the first infusion of IMP (included) from original study to the end of the current study

The following definitions regarding potentially clinically significant abnormality (PCSA) will be applied to laboratory parameters, vital signs and ECG:

- The PCSA values are defined as abnormal values considered medically important by the sponsor according to predefined criteria/thresholds based on literature review and defined by the sponsor for clinical laboratory tests, vital signs, and ECG. These values are provided in [Appendix A](#).
- PCSA criteria will determine which patients had at least 1 PCSA taking into account all evaluations performed, including unscheduled or repeated evaluations.
- Before determining a value as PCSA, the value will be rounded to the precision that the PCSA criterion is defined.

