#### **2.4.7.1.2 Treatment-emergent adverse events**

An overview of TEAEs will be provided to include (potentially related is defined as either “related” or “possibly related” as assessed by the investigator):

- TEAEs
- TEAEs excluding original study
- TEAEs potentially related to study treatment

- TEAEs by the worst severity
- TEAEs leading to treatment discontinuation
- TEAEs leading to study withdrawal
- TEAEs leading to dose reduction
- TEAEs leading to study treatment interruption
- Protocol-defined IARs
- Algorithm-defined IARs
- Treatment-emergent serious adverse events
- Treatment-emergent serious adverse events potentially related to study treatment
- TEAEs with fatal outcome (Deaths)
- Treatment-emergent pregnancies
- TEAEs which are considered symptomatic overdose
- Dose-limiting toxicities (collected in the adverse event log page in e-CRF, see protocol Section 8.1.6 for details)

The following summaries will be produced by primary SOC and PT:

- TEAEs
- TEAEs by the worst severity (ie, mild, moderate, or severe)
- TEAEs potentially related to study treatment
- TEAEs potentially related to study treatment, by the worst severity (ie, mild, moderate, or severe)

The most common TEAEs will be summarized by SOC and PT for patients from pediatric study DFI13803 and for patients from adult study DFI13412 in separate tables. The criteria of most common TEAEs are the following, which will be applied to the two populations separately:

- the number of events of a preferred term is more than or equal to 2% of the number of all TEAEs in the population, AND
- the number of patients who had this event is more than or equal to 2.

For the above summary for patients from pediatric study, it will be summarized by age cohort and overall.

TEAEs by the latest infusion dose immediately preceding the start of AE will be provided by SOC and PT.

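### TEAE status depends on start date alone, so a non-serious worsening is either in no TEAE table (onset before treatment) or not credited to the extension (onset in the original study)

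*SAP*

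**What the plan says.** - **Definition.** SAP 2.4.7.1.1 says TEAEs "will be defined as AEs that started during the on-treatment period – either in this study or in the original study". SAP 2.4.7 sets that period as "the time from the first infusion of IMP (included) from original study to the end of the current study". Neither the SAP nor Protocol 11.6.3.1 adds worsening as a route to treatment-emergent status. Protocol 11.6.3.1 lists pretreatment events apart from TEAEs.
- **Severity.** SAP 2.4.7.1.1: "If an AE worsens in severity, only the worst severity is captured on the AE log page in the e-CRF".
- **Carried-over events.** Protocol 10.5 brings these into the extension: "Adverse events that started during the previous study which are ongoing at the time the patient signs the written informed consent should be reported in" [the extension]. SAP 2.1.3.1 has them copied into this database and followed. SAP 2.4.7.1.1 then reports each as a single event.
- **Seriousness.** SAP 2.4.7.1.1 splits an event that becomes serious into two records with the same number and starts the serious record on the day it became serious. Severity has no counterpart.
- **Pooling.** SAP 2.4.7: unless specified otherwise, "the displays will include the original study data along with data collected in this study".
- **Extension-only outputs.** One overview row in SAP 2.4.7.1.2, "TEAEs excluding original study", and in SAP 2.4.7.1.1 a "separate listing of AEs, SAEs and IARs that started only after the first infusion in this extension study will be provided".
- **Dose.** SAP 2.4.7.1.2 assigns each TEAE to the last infusion dose before it started. Protocol 11.6.3.1 uses the dose before or during the occurrence of the event.
- **Unknown onset.** SAP 2.4.7.1.1 and 2.6.2 treat such events as treatment-emergent.

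**The concern.** The primary objective is safety under long-term exposure, and every patient is a rollover who may enter with continuing events. Late toxicity in such patients could appear as a continuing problem getting worse as well as a new event. The planned rules follow new starts and new seriousness, but not new severity.

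At stake are two readings of the safety results. The first is whether the TEAE tables include all on-drug deterioration. The second is whether the outputs meant to isolate the extension show what happened there, at the dose then in use. In both, an omission can only lower the count.

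**Working it through.** No power, sample-size or rate formula applies, and the plan gives no figure to reproduce. The check applies the SAP rules to each way an event can worsen.

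| Case | Pooled TEAE tables | Extension-only row and listing | Date and dose |
|---|---|---|---|
| A. Began on treatment in the original study; worsens in the extension, stays non-serious | Included, at worst severity | Not in the listing; not in the row if it is read by onset | Original onset, onset dose |
| B. As A, but becomes serious in the extension | Included; serious part in the SAE table | Serious part qualifies | Serious part dated in the extension |
| C. Known onset before the first infusion of the original study; worsens on drug, stays non-serious | Not included | Not included | Pre-treatment onset; not in the by-dose TEAE table |
| D. As C, but becomes serious on treatment | Serious part counts as a treatment-emergent SAE | Serious part qualifies if it became serious after the first extension infusion | Serious part re-dated |
| E. Onset cannot be placed | Included by default | Not determined by the default rule | Not determined |

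Cases A and C are the gap.

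**Case C.** The overview rows for treatment discontinuation, interruption and dose reduction are all TEAE rows (SAP 2.4.7.1.2). A pre-treatment event that worsens and leads to one of these actions is therefore missing from the matching row. SAP 2.5 would still give a narrative if it led to permanent discontinuation.

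**Case A.** What is lost is attribution. The event is counted at its worst severity, but under its old onset and at the dose given before that onset. The onset dose may differ from the dose at worsening.

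**Size.** The number of case A or case C events is not in the documents. The only extension-only output with an incidence is the overview row. With the approximately 25 patients of Protocol 11.2:

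- one patient not counted = 1/25 = 4 percentage points;
- this applies only if that patient has no other TEAE starting in the extension, since otherwise the patient is already in the row.

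Among the 5 patients from DFI13412, shown as a separate subgroup under SAP 2.4, the same conditional shift is 1/5 = 20 points. The other extension-only output is a listing and has no incidence to shift.

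**The case against.** The strongest reply is that the SAP pools both studies on purpose. Onset in either study counts, and severity is tabulated at its worst. An event that began on drug in the original study and turned severe years later is in the SOC and preferred-term tables as severe. If it led to discontinuation, interruption or dose reduction, it falls in those rows too. This stands. A reader might infer that worsened carried-over events disappear from the safety tables; for onsets on treatment, the documents show otherwise.

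A reader might also infer that no worsened pre-treatment event can become treatment-emergent. The seriousness split rules that out for events that become serious, and the default rule covers unknown onsets.

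Three further points stand in part:

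- Laboratory, ECG and vital-sign changes are summarised by visit, PCSAs use all evaluations including unscheduled ones, and the liver-threshold events are listed and trigger narratives (SAP 2.4.7, 2.4.7.1.3, 2.4.7.2 to 2.4.7.4, 2.5). Worsening that shows in those measurements is visible at its own date. Symptoms and diagnoses without such a measurement have no such second view.
- The SAP does not define how the extension-only row excludes the original study. Exclusion by onset is the natural reading, in line with the listing, but it is a reading.
- With no date of severity change stored, a new definition cannot restore the time or dose of past worsenings. This limits the remedy and does not remove the gap.

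**Conclusion.** The point holds for events that worsen without becoming serious, in two forms:

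1. If onset is known to precede the first infusion of the original study, the event is in no TEAE table, pooled or extension-only. This follows directly from the stated definition.
2. If onset was on treatment in the original study and the worsening came in the extension, the pooled worst-severity counts are intact. The event is absent from the extension-onset listing and, assuming exclusion by onset, from the extension-only row. It also stays at its onset dose.

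The frequency is unknown and could be zero. It would be wrong to infer that every event ongoing at consent is affected, since only those that later worsen non-seriously are. It would also be wrong to infer that each one moves an extension incidence by 4 points: that figure belongs to one overview row and is conditional on the patient having no other extension-onset TEAE. The direction is certain, because the rule can only omit events. The change is worth making because the study's main question is long-term safety and the SAP already applies the same principle to seriousness.

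**What to change.** 1. In SAP 2.4.7.1.1, define a TEAE as an AE that started, or increased in severity, on or after the first infusion of the original study.
2. For the extension-only row and listing, also flag a carried-over AE whose worst severity in this study exceeds the severity in the original-study record. This assumes that record was fixed at rollover; the original study's CRF rules are not in these documents and should be checked. Define the row explicitly.
3. State the limits. The comparison finds worsening after rollover only, and the date and dose of such past worsenings cannot be recovered. A pre-treatment event that worsened within the original study can be reclassified only if that study's data show the change.
4. For the remaining follow-up, record the date of each severity increase, or open a linked record under the same AE number as in the seriousness split. Dose and time are then assigned at worsening, and the shared number prevents double counting.

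Cost: SAP wording, one comparison of two existing AE datasets, and a CRF field or completion note. The SAP is written to Amended Protocol 04 while the protocol is at 07, so the wording can go into an update that is needed anyway. The downsides are slightly higher AE counts and a change of recording convention part-way through the study, which the CSR should note.

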#### 2.4.7.1.3 *Adverse events of special interest*

**Protocol-defined IAR:** The following summaries will be produced by primary SOC and PT:

- Protocol-defined IARs
- Protocol-defined IARs by the worst severity
- Protocol-defined IARs started during infusion
- Protocol-defined IARs started between 0 hours (exclusive) and 3 hours (exclusive) post end of infusion
- Protocol-defined IARs started between 3 hours (inclusive) and 24 hours (inclusive) post end of infusion
- Protocol-defined IARs started between 24 hours (exclusive) and 72 hours (inclusive) post end of infusion
- Protocol-defined IARs started after 72 hours post end of infusion

Additionally, Hypersensitivity IARs will be summarized by primary SOC and PT.

In case there are IARs identified by the sponsor (before database lock) that the investigator did not agree to be an IAR, sponsor-identified IARs may be added to the list of investigator-identified IARs to define the protocol-defined IARs, and additional summaries may be produced.

**Algorithm-defined IAR:** The summary of algorithm-defined IARs by primary SOC and PT will be provided.

**Pregnancy:** Pregnancies will be provided as part of patient narrative.

**Symptomatic overdose:** The symptomatic overdose data will be provided as part of patient narrative.

**Quantifiable Dose Limiting Toxicities defined based on laboratory values:** As defined in [Section 2.1.3.1](#), the Quantifiable Dose Limiting Toxicities will be provided in a data listing.

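### Splitting an adverse event that becomes serious into two records counts it twice at its worst severity in event-based tables, and can add a re-dated serious record to a later infusion-reaction row or dose

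*SAP*

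**What the plan says.** All the split rules are in SAP 2.4.7.1.1 (Definitions). An AE with a recorded date of becoming serious is handled so that "this AE will be split into two AEs - one non-serious, and one serious AE - with the same AE number".

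- **Serious record:** "Serious AE: AE start date will use the date the event became serious". No clock time is mentioned.
- **Non-serious record:** "Non-serious AE: AE end date, AE outcome, date of death or hospitalization, autopsy information, criterion for serious adverse event (SAE) will be blank". Severity, relationship and the IAR flag are not among the fields changed. Action-taken fields are allocated case by case with the safety monitor.
- **Severity:** "If an AE worsens in severity, only the worst severity is captured on the AE log page in the e-CRF".
- **Counting:** "Adverse event summaries will include the number of events (N), number (n) and percentage (%) of patients experiencing an adverse event". The section gives no instruction to collapse the two records on their shared number.

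The same section takes the opposite approach to AEs continuing from the original study: each "will be reported as one AE avoiding duplication of the same AE in two database".

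Three sets of outputs depend on when the AE started:

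- the timing rows for protocol-defined IARs in SAP 2.4.7.1.3, for example "Protocol-defined IARs started between 24 hours (exclusive) and 72 hours (inclusive) post end of infusion", repeated by place of infusion in 2.4.7.1.6;
- the algorithm-defined IAR in SAP 2.1.3.1, which runs from infusion start to 24 hours after infusion end. An AE with no time counts if it is dated on the infusion-end date or the next day;
- the dose table in SAP 2.4.7.1.2: "TEAEs by the latest infusion dose immediately preceding the start of AE will be provided by SOC and PT".

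**The concern.** Safety is the primary objective, and only about 25 patients are expected. In tables of that size, one duplicated or re-dated serious record is visible. Two things go wrong if the rule is programmed as written.

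First, one clinical event becomes two events under one preferred term. Both carry the worst severity, even if the non-serious phase was mild, because the e-CRF keeps no earlier grade.

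Second, outputs meant to show how soon after an infusion a reaction began, and at which dose, would for the serious record show when it met a seriousness criterion. That is a different quantity from onset.

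**Working it through.** The plan states no figure on this point, so there is nothing to reproduce. The check applies the SAP's rules to one illustrative record and to illustrative counts. Clock times and counts are assumptions.

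**1. Event counts.** One e-CRF event that becomes serious gives N = 1 + 1 = 2. Both records keep the worst severity, so a severe event adds 2 to the severe row. The patient still counts once per term, so patient n and % for TEAEs do not change. The SAE table receives one record.

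**2. Common-TEAE rule (SAP 2.4.7.1.2).** A term qualifies if its events are at least 2% of all TEAEs in the population and at least 2 patients had it. With e events of the term among M in total, and s of the term's events split, the share moves from e/M to (e + s)/(M + s).

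| e | M | s | Before | After | Event test |
|---|---|---|---|---|---|
| 3 | 199 | 1 | 1.51% | 4/200 = 2.00% | fails, then passes |
| 9 | 500 | 2 | 1.80% | 11/502 = 2.19% | fails, then passes |
| 9 | 500 | 1 | 1.80% | 10/501 = 1.996% | fails both times |

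A split in another term works the other way: 4/200 = 2.00% passes, but 4/201 = 1.99% fails.

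**3. IAR timing.** Assume an infusion from 10:00 to 13:40 on day 0, onset at 12:00 that day, and only a date for becoming serious. The non-serious record is always in the during-infusion row and always an algorithm-defined IAR. The serious record behaves as follows.

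| Became serious | Algorithm-defined IAR? | Timing row |
|---|---|---|
| Day 0 | yes | during infusion, up to 3–24 h |
| Day +1 | yes | 3–24 h or 24–72 h |
| Day +2 | no | 24–72 h |
| Day +3 | no | 24–72 h or >72 h |
| Day +4 or later, before the next infusion | no | >72 h |

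On days 0, +1 and +3 a date alone cannot settle the hour-based row, and the SAP gives no rule for choosing.

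**4. The reverse error.** Suppose an AE begins outside any infusion window and becomes serious on the end date of a later infusion, or the next day. With no time recorded, the missing-time rule makes the serious record an algorithm-defined IAR, although onset was unrelated in time.

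**5. Dose.** Infusions are every 14 ± 3 days (Protocol 8.1.1). The event must usually become serious about 14 − 3 = 11 or more days after the preceding infusion before another one intervenes. The serious record is then attributed to that later infusion. The dose shown differs only if the two doses differ.

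**The case against.** The strongest reply is that little is lost and safeguards exist. Most of its factual content stands.

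- **The reaction is not moved out of its window.** A reader might infer that it is. Only the serious record is re-dated; the non-serious record keeps the true onset and the IAR flag. Protocol-defined IAR status is a recorded judgement with no upper time limit (Protocol 10.5.1.3.2, SAP 2.1.3.1). The defect is an extra, later record.
- **Patient incidence is not inflated.** Patient n and % for TEAEs are unaffected, and Protocol 11.6.3.1 counts repeat occurrences once per patient. That rule does not govern the event count N that the SAP adds.
- **No share of serious IARs can be said to be misplaced.** A reader might infer that all serious reactions could sit in the wrong row. None of the planned IAR summaries is by seriousness, and the documents do not say how often an IAR becomes serious late.
- **The two errors do not coincide in the algorithm-defined IAR table.** For a reaction with onset in the window, a serious date on day +2 or later leaves one correctly placed record there. Double counting from the same infusion needs day 0 or day +1.
- **A change of dose is uncommon.** Patients normally stay on one dose in this study (Protocol 8.1.3). It mainly needs a dose reintroduction, or an escalation in the original-study data that the safety displays include (SAP 2.4.7).
- **Records are traceable.** The AE number is shared, and SAEs and protocol-defined IARs both trigger narratives (SAP 2.5).

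These points limit the size of the problem. They do not answer it: a shared number allows de-duplication, but the SAP does not ask for it, and narratives do not correct a table.

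**Conclusion.** The point holds for event-level results. Followed as written, SAP 2.4.7.1.1 adds one event, at worst severity, for each AE that becomes serious. This affects N in the TEAE, relatedness, severity and protocol-defined IAR summaries, and it enters the 2% common-TEAE rule. Near the threshold, a single split can change which terms are listed, provided the two-patient condition is also met.

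The timing effects are conditional. The serious record may add an entry to a later protocol-defined IAR row. It is not an algorithm-defined IAR if the event became serious 2 or more calendar days after the infusion ended, unless the date falls on or the day after a later infusion, when it can wrongly become one. It takes a later infusion's dose only if another infusion intervenes.

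This rests on two readings: severity, relationship and the IAR flag carry over to both records because nothing changes them, and the serious record has no clock time because only a date is described. The number of affected events is unknown and probably small. The documents do not support a claim that serious reactions disappear from their infusion window or that patient percentages are inflated.

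**What to change.** Replace the split in SAP 2.4.7.1.1 with a rule to this effect: each AE number contributes one record, with its original onset date and time, its recorded worst severity and a seriousness flag. That record is used for all TEAE, severity, relatedness, common-TEAE, IAR-timing, algorithm-defined IAR and latest-dose tables, including those by place of infusion. The date of becoming serious is kept as a separate variable and used only in the SAE table, SAE listing and narratives.

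This preserves the purpose of the split, which is to show when an event became serious. With one record, the action-taken fields no longer need to be divided between two halves. The cost is a short SAP revision and a simpler derivation, with no new data collection. Make the change before database lock.
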